## **Exclusion Criteria**

To be eligible for entry into the study, patients must not have any of the conditions listed below:

- Be pregnant or lactating
- Allergies or clinical conditions precluding safe use of Omegaven™
- Parent or guardian or child unwilling to provide consent or assent
- Inability or unwillingness on the part of the parent/guardian or child to follow clinical recommendations of the Intestinal Rehabilitation Program

### **Omegaven™ Dosages**

Pharmacy-International will be the Drug Supplier for this study. The Omegaven™ will be delivered to the study site, where it will be stored in the hospital pharmacy, at the appropriate temperature and prepared for infusion.

### **Dosing Instructions and Schedule**

During the treatment period, patients will receive an approximate daily infusion of Omegaven™ at a dose of 1g/kg/day, to be infused over 12-24 hours.

### **Omegaven™**

The dose of Omegaven™ (1g/kg/d) will be administered by the nursing staff when the patient is in the hospital and administered by the patient (adult) or parent, if patient is a child, when the patient is outpatient during treatment.

In the event that a patient is unable to achieve adequate calories parenterally and is unable to tolerate enteral feeds, it may be necessary to evaluate whether or not the patient should continue the study with Omegaven™ or resume therapy with conventional fat emulsions so that additional parenteral fat calories can be given.

### **Monitoring and Possible Dose Reductions**

In addition to standard nutritional monitoring, essential fatty acids will be sent monthly and serum triglyceride levels will be sent weekly. If lipid intolerance develops, defined as serum triglyceride levels > 200 mg/dL, the following will be considered prior to reducing the dose:

- a) If the level was obtained while the patient was receiving a continuous 24- hour infusion of Omegaven™, the total dose will be infused over 20 hours, and a repeat serum triglyceride level obtained prior to resuming the infusion 4 hours later.
- b) Other sources of lipid intolerance will be considered and addressed (drugs, renal disease)

If the triglycerides continue to remain high despite the aforementioned interventions, a dosage reduction of 25% of the current dose will be considered.

### **Duration of Therapy**

Patients will remain on Omegaven™ until weaned from PN and may continue monotherapy with Omegaven™ as an additional source of calories after the dextrose/protein portion of PN is discontinued.

In the event that a patient is listed for a liver or liver/intestinal transplant and an organ becomes available, the participation in this protocol will not preclude them from receiving the transplant.

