## ABSTRACT

In the United States, patients dependent upon parenteral nutrition (PN) receive parenteral fat emulsions composed of soybean oils. Lipids are necessary in PN-dependent patients due to their high caloric value and essential fatty acid content. They have been implicated in predisposing patients to PN-associated liver disease, and children requiring prolonged courses of PN are at risk for developing PN-associated liver disease. Animal studies have shown that IV fat emulsions such as fish oil that are high in eicosapentaenic and docosahexaenoic acid reduce impairment of bile flow which is seen in cholestasis caused by conventional fat emulsions. We hypothesize that a fat emulsion comprised of omega-3 fatty acids (i.e., fish oil) such as Omegaven™ will be well tolerated and will reduce the inflammatory effect in the liver of prolonged PN exposure, with the potential of reversing any hepatic dysfunction due to PN/IFE use. By administering Omegaven™ in place of conventional phytosterol/soybean fat emulsions we may reverse or prevent the progression of PN associated cholestasis and thus allow the patient to be maintained on PN until they are able to ingest adequate nutrition enterally.

All patients in the Intestinal Rehabilitation Program at UNMC with an abnormal serum bilirubin (>2mg/dL), receiving PN and not meeting an exclusion criteria will be approached for enrollment. Upon enrollment, the PN lipid source will be switched to Omegaven, and patients will continue to be followed in standard fashion for ongoing intestinal rehabilitation. Patients will continue to have regular follow-up including laboratory evaluation at least once weekly, with periodic radiologic and endoscopic evaluation as per our standard of care. As hypertriglyceridemia is a possible side effect of Omegaven, weekly triglyceride levels will be added to regular labs. Patients will be continued on Omegaven until weaned from intravenous lipids per standard of care. Clinical data will be collected prospectively and will be compared with historical controls.

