We propose to conduct a prospective evaluation of the use of Omegaven™ for the provision of parenteral lipid calories in concert with an active ongoing program of intestinal rehabilitation. Our main outcome of interest will be need for small bowel transplantation, with secondary outcomes including improvement in clinical measures associated with PNALD and need for liver transplantation. This study will be conducted in both pediatric and adult intestinal rehabilitation patients.

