### Objectives

The primary objective of this study is to evaluate the need for small bowel transplantation. Clinical data will be collected prospectively and will be compared with historical controls.

Secondary objectives are to determine if there are improvements in clinical measures associated with established parenteral nutrition- associated liver disease (PNALD).

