## **Study Design**

This study will be a prospective, non-randomized, open-label study of Omegaven™ with a total enrollment of 100 patients, for provision of parenteral lipid calories. The study cohort, receiving the PN at 1g/kg/day, will be compared to historical controls at UNMC where parenteral lipid calories were provided exclusively through soybean-based formulations, as well as, assessing the study cohorts need for small bowel and liver transplantation.

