## **Inclusion Criteria**

The first 100 eligible patients must meet the conditions listed below:

- Patients must be enrolled in the Intestinal Rehabilitation Program at the University of Nebraska Medical Center, and:
- Be unable to meet nutritional needs solely by enteral nutrition and be expected to require PN for at least another 30 days
- Have clinical evidence of parenteral nutrition associated liver disease (PNALD) as defined as direct bilirubin of 2mg/dl or more. A liver biopsy is not necessary for treatment.
- Signed patient informed consent.

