## Statistical Analysis

Data from the two sets of patient population will be pooled and compared (i.e., current protocol patients prescribed Omegaven™ PN compared to historical controls where parenteral lipid calories were provided exclusively through soybean-based formulations). Potential for effect in different patient populations will be minimized by matching patients enrolled in the Omegaven™ protocol to historical controls. Frequency matching will be utilized given the difficulty of paired matching in this patient population. Specific matching criteria will include gender, age, etiology of short bowel syndrome, and severity of liver disease (parenteral nutrition- associated liver disease).

Continuous data will be expressed as mean +/- SEM. A two-way repeated measure ANOVA will be used to compare differences in the two groups with respect to changes between the Evaluation assessment and the subsequent analyses performed at Treatment and Treatment/Follow-up Assessments. Incidence of adverse events in each treatment arm will be compared using Fisher's exact test. Univariate and multivariate analysis will be used to identify baseline factors that may influence outcome. A P-value <0.05 will be considered statistically significant.

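### Transplant listing at entry is neither recorded nor balanced against the historical controls, although patients already listed for an intestine-containing graft may enrol and start at high risk of the primary outcome

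*Combined protocol and SAP*

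**What the plan says.** The Objectives section states: "The primary objective of this study is to evaluate the need for small bowel transplantation". Background and Rationale says the same ("Our main outcome of interest will be need for small bowel transplantation") and makes liver transplantation secondary. Neither says whether need means evaluation, listing or receipt of a graft, and neither gives a time point.

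Recruitment is broad. The Abstract says that all patients of the rehabilitation program with raised bilirubin, "receiving PN and not meeting an exclusion criteria will be approached for enrollment". The liver criterion under Inclusion Criteria is "Have clinical evidence of parenteral nutrition associated liver disease (PNALD) as defined as direct bilirubin of 2mg/dl or more". Exclusion Criteria opens with "To be eligible for entry into the study, patients must not have any of the conditions listed below" and gives four items: pregnancy or lactation, allergy or a condition ruling out safe use, lack of consent or assent, and unwillingness to follow the program's recommendations. Transplant listing appears in neither list.

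Duration of Therapy contains the clause "In the event that a patient is listed for a liver or liver/intestinal transplant and an organ becomes available" and adds that being in the study does not stop the patient from receiving the organ.

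Under Study Design, the cohort "will be compared to historical controls at UNMC where parenteral lipid calories were provided exclusively through soybean-based formulations". Statistical Analysis plans frequency matching: "Specific matching criteria will include gender, age, etiology of short bowel syndrome, and severity of liver disease (parenteral nutrition- associated liver disease". It also plans univariate and multivariate analyses of baseline factors but names none. The Evaluation Assessments do not include listing status.

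**The concern.** A patient already on the waiting list for an intestine-containing graft differs from one who is not, and the difference bears directly on the primary outcome. If need means listing, that patient has the event before the first dose. If it means receipt of a graft, the patient starts at high risk, and the timing depends partly on when an organ becomes available.

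Listing at entry is a realistic state here. Background and Rationale places the program alongside small bowel transplantation in one intestinal failure service, and describes patients limited by progressing liver disease. Entry requires liver disease that is already established.

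The comparison is not randomized, so only the matching and any adjustment can balance listing status, and neither names it. If the listed share differs between the cohort and the controls, the groups will differ on the primary outcome even if the lipid source makes no difference.

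**Working it through.** **No figure of the plan to reproduce.** The enrolment of 100 comes without power, effect size, control event rate, number of controls or listed share. What follows is a sensitivity calculation.

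**From the documents:** 100 treated patients (Study Design); significance at P < 0.05 (Statistical Analysis).

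**Assumed:** 100 controls; a two-sided test; a two-proportion comparison, because Statistical Analysis names no test for the transplant outcome; and no drug effect. Let *s* be the share listed at entry, *L* the event risk if listed and *u* the risk if not, with *L* and *u* the same in both groups.

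**Event rate in a group:** *sL* + (1 − *s*)*u*. With *L* = 0.8 and *u* = 0.2:

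- *s* = 0.1: 0.08 + 0.18 = 0.26
- *s* = 0.2: 0.16 + 0.16 = 0.32
- *s* = 0.3: 0.24 + 0.14 = 0.38

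**False difference** (control minus treated): (*s* control − *s* treated) × (*L* − *u*). For 10% v 30% listed this is 0.2 × 0.6 = 12 points. For 10% v 20% it is 0.1 × 0.6 = 6 points.

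**Chance of P < 0.05 with no drug effect** (normal approximation, pooled variance under the null). For 26% v 38% the pooled rate is 0.32.

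- Null SE = √(0.32 × 0.68 × 2/100) = 0.0660, so the critical difference is 1.96 × 0.0660 = 0.129.
- SE under the actual rates = √(0.26 × 0.74/100 + 0.38 × 0.62/100) = 0.0654.
- Φ((0.12 − 0.129)/0.0654) is about 0.44; the other tail is negligible.

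| Listed, Omegaven v control | *u* | *L* | Event rates | Chance of P < 0.05 |
|---|---|---|---|---|
| 20% v 20% | 20% | 80% | 32% v 32% | 5% |
| 10% v 20% | 20% | 80% | 26% v 32% | 15% |
| 10% v 30% | 20% | 80% | 26% v 38% | 44% |
| 30% v 10% | 20% | 80% | 38% v 26% | 44%, against Omegaven |
| 10% v 30% | 20% | 100% (listing counts as the event) | 28% v 44% | 66% |

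**Range.** With *u* from 10% to 30% and *L* from 60% to 100%, a 10% v 30% imbalance gives false differences of 6 points (0.2 × 0.3) to 18 points (0.2 × 0.9), and a 14% to 81% chance of P < 0.05. A 10% v 20% imbalance gives 3 to 9 points and 7% to 32%. With equal listed shares the chance returns to 5%.

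**The case against.** Several points on the other side have force.

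- **Timing of listing.** A reader might infer from Duration of Therapy that participants were listed before enrolment. The clause does not say so. It fits listing during treatment equally well, and it also covers liver-only listing, which is not the primary outcome. That listed patients may enrol follows from the open recruitment and the silence of the entry criteria. How many would do so is unknown, and it could be few.
- **Need already decided.** A reader might infer that listed patients have met the outcome and cannot benefit. That holds only if need means listing, which the protocol never states. The Hypothesis is that established liver disease can be reversed, so a listed patient might improve and come off the list.
- **Dilution.** For the same reason, it does not follow that equal listed shares must hide a true effect. Suppose unlisted rates of 40% v 20%, 100 per group and every listed patient counted as an event. Power then falls from 88% with none listed to 63% with 20% listed. This rests on treatment making no difference to listed patients, which the documents do not establish if receipt is the event.
- **Existing safeguards.** Liver disease severity plausibly drives liver/intestinal listing, and it is a matching factor. The planned multivariate analysis could take in listing status, and listing data may well be available within the same service. This protection is partial: severity has no stated measure, frequency matching on four other factors does not ensure balance on listing, and the multivariate analysis names no covariate.
- **Direction.** Nothing in the documents shows that the controls had more listed patients, so a bias in favour of Omegaven cannot be presumed.

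**Conclusion.** The point holds as a gap in balance. Under the plan as written, a strong baseline predictor of the primary outcome is not called for at baseline and is not named in the matching or the adjustment. Any difference in listed share carries straight into the primary comparison, in either direction.

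The size is unknown. The 12-point and 6-point false differences rest on assumed risks of 80% and 20% and on assumed listed shares; the error rates also assume 100 controls. None of these calculations credits severity matching with any balancing of listing status. The documents do not show that listed patients were beyond benefit, that listing preceded enrolment in any given case, or that the bias favours Omegaven. Nor do they require the primary comparison to be confined to unlisted patients, unless listing itself is chosen as the event. This is a low-cost improvement worth making, not evidence that the comparison is invalid.

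**What to change.** 1. In Objectives, state whether the event is listing for, or receipt of, an intestine-containing graft.
2. Add transplant listing status, type and date to the Evaluation Assessments. Define an index date for the historical controls and record the same items at that date.
3. In Statistical Analysis, add listing status at entry to the frequency-matching factors, or stratify or adjust for it in the primary comparison.
4. Report a sensitivity analysis in patients not listed for an intestine-containing graft at entry. Show the outcomes of listed patients separately: transplanted, removed from the list, died, still waiting.
5. If listing is the event, leave patients already listed out of that comparison, because they are not at risk of it.

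Enrolment and care do not change. The costs are chart review of controls against an index date that does not yet exist, somewhat harder matching, and fewer than 100 Omegaven patients in the unlisted-only analysis if any are listed. One limit remains: listing practice may have changed between the control era and the study, so balance on listing may not fully equalise underlying need.

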### **Disruption of Therapy**

In the event that treatment with Omegaven™ cannot be administered (i.e. loss of central venous catheter access, fluid restrictions, need to administer an incompatible medication/blood product), the infusion of Omegaven™ may be interrupted and resumed when the conflicting situation is resolved. Some potential interventions that can be used include:

Situation	Possible Solution
Loss of central venous access	Administer via peripheral route
Fluid restriction	Consult with pharmacy to concentrate PN, medications to allow for administration
Limited access, need to administer incompatible medications	Stop Omegaven™ infusion, flush catheter with either NS or dextrose, administer incompatible medication, flush catheter, resume infusion; may be necessary to infuse Omegaven™ over greater than 12 hours (use multiple syringes so as to keep maximum hang time of Omegaven™ source container less than 12 hours)

Treatment will be discontinued and not restarted if the patient experiences a significant allergic reaction. Omegaven™ should not be administered to patients allergic to fish or egg protein.

### **Discontinuation of Therapy**

Patients will continue to be followed by the UNMC Intestinal Rehabilitation Program upon discontinuation of therapy with Omegaven™ until they are completely free of any rehabilitation needs and are tolerating a full diet by mouth.

### **Side Effects (that may lead to Disruption or Discontinuation of Omegaven™):**

The infusion of Omegaven™ can lead to prolonged bleeding time and an inhibited platelet aggregation. The administration of Omegaven™ should be stopped or reduced if there is a marked increase in blood glucose levels during infusion. Undesirable effects that are seen during infusion of Omegaven™ that may also occur with conventional fat emulsions (i.e., Intralipid) include:

Slight rise in body temperature, Heat sensation and/or cold sensation, Chills, Dyspnea, Flushing or cyanosis, Lack of Appetite, nausea, vomiting, Headache, pain in chest, bone pain, Priapism, Increase/decrease in blood pressure, Anaphylactic reactions/erythema

Other expected adverse events that are common to all patients with short bowel syndrome, regardless of the type of fat emulsion they receive, include blood stream infections and re-admittance to hospital. Causes for re-hospitalization include dehydration, bloodstream infections, electrolyte abnormalities, bowel obstruction, and central venous catheter malfunction.

### **Contraindications to Omegaven™ include the following:**

Impaired lipid metabolism, Severe hemorrhagic disorders, Unstable diabetes mellitus, Collapse and shock, Stroke/embolism, Recent cardiac infarction, and Undefined coma status

### **Storage and Handling of Omegaven™**

All Omegaven™ received and dispensed by the Investigator or his designee will be inventoried and properly accounted for throughout the study. The Omegaven™ will be stored in a refrigerated, secured area, with controlled access until administration. The patient will be instructed to store the Omegaven™ in a similar fashion once they leave the in-house setting and are discharged home.

## **Patient Discontinuation**

The Investigators may discontinue an individual patient from the study at any time. They may voluntarily withdraw at any time. A patient may experience Dose Modification, Disruption of Therapy, or Discontinuation of Therapy from the study for the following medical or administrative reasons.

### **Dose Modification for Lipid Intolerance -**

- If lipid intolerance develops, defined as serum triglyceride levels > 200 mg/dL, all sources of lipid intolerance should be considered and addressed (drugs, renal disease, etc). If the triglycerides continue to remain high despite the aforementioned interventions, a dosage reduction of the current dose will be considered.

### **Disruption of Therapy -**

- In the event that Omegaven™ cannot be administered (i.e. loss of central venous catheter access, fluid restrictions, need to administer an incompatible medication/blood product), the infusion of Omegaven™ may be interrupted and resumed when the conflicting situation is resolved.

### **Discontinuation of Therapy –**

- In the event that a patient is unable to achieve adequate calories parenterally and is unable to tolerate enteral feeds, it may be necessary to evaluate whether or not the patient should continue the study with Omegaven™ as monotherapy or resume therapy with conventional fat emulsions so that additional parenteral fat calories can be given.
- Adverse Event (AE) – Any patient with anaphylactic or allergic reactions to Omegaven™ will not continue treatment and will be withdrawn from the protocol.
- Inter-current Illness – If a patient develops an illness during the course of the study that is not associated with the condition under study and that requires treatment inconsistent with the protocol requirements (such as an interruption of regular participation in the study), the patient may be discontinued from further participation in the study. A patient may also be discontinued from the study if he develops an inter-current illness or complication that in any way justifies his withdrawal from the study. However, if an inter-current illness develops which can be managed without significant interference with the requirements of the protocol, the patient need not be discontinued.
- The patient will complete treatment with Omegaven™ in this study when he/she is completely off PN, develops a contraindication for further use, or the patient/family requests to be removed from the study.

## Statistical Analysis

Data from the two sets of patient population will be pooled and compared (i.e., current protocol patients prescribed Omegaven™ PN compared to historical controls where parenteral lipid calories were provided exclusively through soybean-based formulations). Potential for effect in different patient populations will be minimized by matching patients enrolled in the Omegaven™ protocol to historical controls. Frequency matching will be utilized given the difficulty of paired matching in this patient population. Specific matching criteria will include gender, age, etiology of short bowel syndrome, and severity of liver disease (parenteral nutrition- associated liver disease).

Continuous data will be expressed as mean +/- SEM. A two-way repeated measure ANOVA will be used to compare differences in the two groups with respect to changes between the Evaluation assessment and the subsequent analyses performed at Treatment and Treatment/Follow-up Assessments. Incidence of adverse events in each treatment arm will be compared using Fisher's exact test. Univariate and multivariate analysis will be used to identify baseline factors that may influence outcome. A P-value <0.05 will be considered statistically significant.

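### Historical controls are frequency-matched on four factors, but no stated group comparison uses those factors

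*Combined protocol and SAP*

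**What the plan says.** The Study Design section describes a "prospective, non-randomized, open-label study" of 100 patients, compared with historical controls at the same centre. The Statistical Analysis section relies on matching to make the two populations comparable. It gives four factors ("Specific matching criteria will include gender, age, etiology of short bowel syndrome, and severity of liver disease") and the type of matching: "Frequency matching will be utilized given the difficulty of paired matching in this patient population".

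Three analyses follow in that section:

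- Continuous outcomes: "A two-way repeated measure ANOVA will be used to compare differences in the two groups with respect to changes between the Evaluation assessment" and the later assessments.
- Safety: "Incidence of adverse events in each treatment arm will be compared using" Fisher's exact test.
- Baseline factors: "Univariate and multivariate analysis will be used to identify baseline factors that may influence outcome".

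Neither of the first two is said to include, or stratify by, the matching factors. The third names no group term, no list of covariates and no adjusted group effect. No other section describes an adjusted comparison. The plan also gives no age bands, severity categories, number of controls or balance check.

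**The concern.** Frequency matching aims at similar shares of each category in the two groups. It does not pair patients, and it need not give exact balance, least of all when categories are broad and the population includes both children and adults. Matching is the only control of confounding that the plan states for the group comparison. A difference in case mix that survives it would be read as an effect of Omegaven, in its favour or against it.

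If the matching works well, there is a different cost. The groups are then more alike on prognosis than the unadjusted standard error assumes, so the test rejects too rarely and loses power. In both situations the stated comparison sets aside information that the plan itself treats as prognostic and must collect anyway.

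**Working it through.** **No figure to reproduce.** The plan gives no power, effect size, SD or number of controls. What follows is an illustration on assumed inputs.

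**Inputs.** From the documents: 100 Omegaven patients and a significance level of 0.05 (taken as two-sided). Assumed: 100 controls (also 50 and 200); R², the share of the variance of the change explained by the four factors, at 0.1 / 0.3 / 0.5; and d, the imbalance left after matching, in SD of the combined prognostic index. The SD of the change is set to 1.

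**Formulas.** With m controls, SE = √(1/100 + 1/m), which is √0.02 = 0.141 for m = 100. Bias = √R² × d. Shift = bias / SE. Given the imbalance, the estimate varies with SD √(1 − R²) × SE, but the unadjusted test uses SE. Hence

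size = P(|N(shift, SD √(1 − R²))| > 1.96).

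**Worked example.** R² = 0.3, d = 0.2: bias = 0.548 × 0.2 = 0.110; shift = 0.110 / 0.141 = 0.775; √(1 − R²) = 0.837. The upper tail starts at (1.96 − 0.775) / 0.837 = 1.42, which gives 7.8%. The lower tail adds less than 0.1 point. Size = 7.9%.

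**Size of the unadjusted test, 100 v 100:**

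| Imbalance d | R² = 0.1 | R² = 0.3 | R² = 0.5 |
|---|---|---|---|
| 0 | 3.9% | 1.9% | 0.6% |
| 0.1 | 4.4% | 3.3% | 2.0% |
| 0.15 | 5.1% | 5.1% | 4.4% |
| 0.2 | 6.1% | 7.9% | 8.7% |

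Setting size to 5% and solving for d gives 0.143 / 0.148 / 0.159. Over 50 to 200 controls the threshold runs from about 0.12 to 0.20. At d = 0.2 the bias is 0.06 / 0.11 / 0.14 SD of the change.

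**Power at exact balance, true effect 0.4 SD, 100 v 100.** Effect / SE = 0.4 / 0.141 = 2.83. Unadjusted power is Φ((2.83 − 1.96) / √(1 − R²)); adjusted power is Φ(2.83 / √(1 − R²) − 1.96).

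| | R² = 0.1 | R² = 0.3 | R² = 0.5 |
|---|---|---|---|
| Unadjusted | 82% | 85% | 89% |
| Adjusted | 85% | 92% | 98% |

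The adjusted row is a best case, because it supposes that the model captures the whole prognostic index.

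**Check by simulation.** With two visits, 100 v 100 and 10,000 runs per case, the unadjusted size was 3.9 / 1.9 / 0.7% at d = 0 and 5.7 / 7.8 / 8.6% at d = 0.2. A model of the change containing the prognostic index and the baseline value stayed between 4.7% and 5.2% at d = 0, 0.1 and 0.2.

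**Which factors count.** A factor that shifts every visit by the same amount cancels in the change and does no harm to the group × time test. R² therefore refers to prediction of the change, not of the level.

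**The case against.** The strongest reply is that the plan is silent rather than wrong. It deals with these factors by design, and a multivariate outcome model that includes group is a natural reading of its last analysis. That stands in part: a reader might infer that the plan rules adjustment out, and the text does not say so. But a search for prognostic factors is not a prespecified group comparison. It leaves open whether group enters, which factors stay, and which result counts. In an open-label study with historical controls, that choice should not wait for the data.

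A second reply is that harm is not shown. This is right. Nothing in the documents indicates an imbalance above 0.14 to 0.16 SD after matching, and nothing rules it out. R² of 0.3 to 0.5 for the change has no support in the text. At R² = 0.1 the effects are small: 6.1% size at d = 0.2, and about 3 points of power at 0.4 SD.

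A third reply is that binary outcomes are less affected, and this also stands. Take a risk of 10% with less severe and 40–50% with more severe liver disease (assumed). A 10-point gap in the severe share then gives a false difference of 0.10 × 30 to 40 points = 3 to 4 points. By exact enumeration, Fisher's test has size 4.4–4.9% with 50 or 100 controls, and 5.9–7.1% with 200. This supports keeping Fisher's test for adverse events.

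Finally, adjusting for the baseline value is debatable in a non-randomized comparison. It can answer a different question from the plain change, and it overlaps with liver-disease severity. It is not needed to adjust for the matching factors.

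**Conclusion.** The point holds as a gap in the stated analysis with an inexpensive improvement. The comparisons as written do not use the matching factors, and no adjusted group comparison is described.

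A reader might infer that the planned tests have inflated type I error or favour Omegaven. The documents do not support that. They give no R², imbalance or number of controls, so neither the direction nor the size of any error can be determined. On the assumed values at 100 v 100, the unadjusted test is conservative below about 0.14 to 0.16 SD of imbalance and exceeds 5% only above it.

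The case for adjusting does not depend on which applies. It recovers precision if balance is good, and removes bias from these four factors if it is not, provided the model is adequate. It does nothing for factors that were not matched or measured.

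Two nearby matters are separate and not part of this point: no test is named for the primary objective, and the end of follow-up is left open.

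**What to change.** In the Statistical Analysis section:

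- For continuous outcomes, model the change from Evaluation at each later assessment with group, visit, group × visit and the four matching factors, adding factor × visit terms where numbers allow. Report the unadjusted result alongside. Adding the factors only as main effects to an ANOVA that keeps Evaluation among the responses would not adjust the group × time test, because such terms shift all visits equally and cancel in the change.
- Treat adjustment for the baseline value as an optional sensitivity analysis.
- For the primary objective ("The primary objective of this study is to evaluate the need for small bowel transplantation"), state that whatever group comparison is adopted will be adjusted for, or stratified by, the matching factors as far as event numbers allow.
- Keep Fisher's exact test for adverse events.
- State that the univariate and multivariate search for baseline factors is exploratory and separate from these comparisons.

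The cost is wording and a few extra parameters. The factors have to be collected for the matching in any case. Etiology may need collapsing into fewer categories, and with few transplants not every factor can be included.
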